6.3 Premedication

All patients may receive steroid or anti-emetics premedication prior to tarloxotinib infusions. The premedication regimen will be determined by the Investigator and may be adjusted at subsequent infusions based on the signs and symptoms observed during or after prior infusions.

Additionally, patients may be discharged with take-home prophylactic medications.

The tarloxotinib Phase 1 and 2 studies demonstrated that tarloxotinib is associated with non-hematologic toxicities. These included mainly low-grade skin rash and diarrhea typical of that observed with EGFR TKIs. For this reason, prophylaxis and treatment for these toxicities should be considered following institutional guidelines, similar to another EGFR TKI such as erlotinib or afatinib.

Infusion-related reactions were observed in patients receiving tarloxotinib. These reactions were characterized by flushing, urticarial skin rash, pruritus, and hypotension occurring during or immediately following the infusion of tarloxotinib. Patients who experienced an infusion reaction with the first dose of tarloxotinib received prophylactic steroids prior to subsequent doses, which reduced the severity of infusion reactions. Therefore, prophylaxis for drug hypersensitivity reactions that may include a glucocorticoid and an anti-histamine may be considered prior to each tarloxotinib dose according to institutional guidelines.

Nausea and vomiting have occurred in patients in the Phase 1 and 2 studies; therefore, antiemetic prophylaxis for minimally to moderately emetogenic regimens should be considered after Cycle 1 Day 1 according to institutional guidelines. Prophylaxis against nausea and vomiting in the tarloxotinib studies was based on metoclopramide as a single agent. If a 5-HT3 antagonist is required, palonosetron should be employed, if possible, as it is considered to have the least potential among 5-HT3 antagonists for QT prolongation.

Confidential and Proprietary

6.4 Potassium Supplementation

Serum electrolytes (including potassium) will be checked prior to each tarloxotinib infusion.

- Tarloxotinib will not be administered if the serum potassium level is < 3.5 mEq/L.
- Patients with a serum potassium of < 3.5 mEq/L will receive potassium replacement per institutional policy (IV and/or oral) and have the scheduled tarloxotinib infusion delayed at least 24 hours and potassium levels rechecked within 1 hour prior to the rescheduled infusion.

All patients who present with a serum potassium level of ≥ 3.5 mEq/L will be given potassium supplementation prior to tarloxotinib infusion based on pre-infusion serum potassium result (Table 5).

Table 5: Potassium Supplementation Guidelines

Pre-infusion Serum Potassium (mEq/L)	Potassium Supplement Strategy		
< 3.5	 Hold tarloxotinib Administer potassium replacement per institutional policy (IV and/or PO) Delay the scheduled tarloxotinib infusion delayed at least 24 hours and potassium levels rechecked within 1 hour prior to the rescheduled infusion 		
3.5 to 4.0	• All patients will be supplemented daily with 20 mEq of potassium (IV or PO).		
> 4.0	Administer potassium replacement per institutional policy (IV and/or PO)		

IV = intravenous; PO = oral

6.5 Treatment and Retreatment Criteria

The result of tumor assessments is not required for the initiation of subsequent cycles, but patients must meet the following criteria before receiving each tarloxotinib infusion. **Note:** all ECG dose modifications will be based on the average manually measured QTcF.

• No QTcF of \geq 601 msec during any previous infusion

Note: Patients with QTcF of ≥ 501 msec and < 601 msec during or following the prior infusion MUST be dose reduced. If QTcF prolongation is \geq Grade 3, an ECG may need to be repeated more frequently during a patient's visit as indicated in Table 7, depending on the degree of the prolongation and per institutional standards.

- Check serum electrolytes
 - Pre-infusion magnesium and calcium in normal range, unless an exception is approved by the Medical Monitor.
 - o If other electrolytes (eg, sodium, chloride) are outside of the normal range, patient can receive tarloxotinib infusion if it is deemed safe per Investigator discretion.
 - o Pre-infusion serum potassium must be ≥ 3.5 mEq/L.
- Pre-infusion ECG

Confidential and Proprietary

- o No evidence of second- or third-degree atrioventricular block
- o QTcF interval of < 450 msec
- Skin rash of \leq Grade 2
- Gastrointestinal toxicity of \leq Grade 2
- Any other clinically significant tarloxotinib-related toxicity must return to at least Grade 2.

All patients not meeting retreatment criteria must be discussed with the Medical Monitor (or designee) and possible dose/schedule modification and/or study treatment discontinuation discussed.

6.6 Treatment Beyond Progression

Patients with disease progression may continue to receive tarloxotinib if, in the opinion of the Investigator, the patient is still benefiting (e.g., asymptomatic systemic progression or local symptomatic progression) following discussion with and approval by the Medical Monitor (or designee). The IRB/IEC will be notified of any planned treatment beyond progression. Patients may receive palliative radiation to disease sites of progression, including brain metastases, following discussion with and approval by the Medical Monitor (or designee).

6.7 Tarloxotinib Dose Modifications

All patients will begin study treatment with a dose level of 150 mg/m^2 based on the body weight measured on Day 1 of each cycle (or within 7 days prior [e.g., Day 22 of the prior cycle]). As described above, tarloxotinib dose calculations do not need to be adjusted within a cycle unless the patient has a > 10% change in body weight. Other dose modifications may be required based on QTc prolongation, infusion-related reactions, and other tarloxotinib-related toxicity as described in:

- Table 7: Treatment Guidelines for QTcF Prolongation
- Table 8: Treatment Guidelines for Infusion-related Reactions
- Table 9: Treatment Guidelines for Tarloxotinib-related Non-Hematologic Toxicity

Dose level reductions will be in a step-wise fashion. The dose level reductions are presented in Table 6. If a patient requires more than 2 dose level reductions, tarloxotinib will be permanently discontinued.

Confidential and Proprietary

Table 6: Tarloxotinib Dose Reductions

	Tarloxotinib Dose (mg/m²)		
Dose Level Reduction	Grade 3 QTc prolongation based on a QTcF \geq 501 msec	IRR and/or hematologic/ non-hematologic toxicity	
1	100	120	
2	75		
3	Discontinue tarloxotinib		

IRR = infusion-related reaction; QTc = corrected QT interval; QTcF = corrected QTc interval as calculated according to Fridericia's formula

Hematologic toxicity has not been associated with tarloxotinib administration to date. However, if Grade 3 or 4 neutropenia or thrombocytopenia considered related to tarloxotinib occurs, then the treatment guidelines for non-hematologic toxicity described in Table 9 should be followed. Dose modifications for anemia (any grade) or for Grade 2 or less neutropenia or thrombocytopenia are not required.

If a tarloxotinib-related toxicity results in a treatment delay of more than 3 weeks (withholding more than 2 doses of tarloxotinib), patients will be removed from study treatment unless otherwise approved by the Medical Monitor.

6.7.1 Treatment Guidelines for QTc Prolongation

Immediate medical management of patients will be based on the following:

- 1. Baseline: A pre-infusion (baseline) ECG will be obtained on all patients, if the automated measurements indicate a QTcF of \geq 450 msec
 - a. The single QTcF will be verified by manually measuring at least 3 complexes within the ECG and determining the average QTcF
 - b. All patients must have a pre-infusion QTcF of < 450 msec by either:
 - i. Calculation using the automated measurements of the first ECG or
 - ii. The manual measurement of a single ECG

If it is determined that the manually read QTcF \geq 450 msec, the Medical Monitor should be contacted to discuss the clinical significance of the reading and to determine if it is appropriate to move forward with the infusion.

2. During treatment: Grade 3 QTc prolongation (any QTcF that is ≥ 501 msec OR > 60 msec QTcF increase relative to pre-infusion) will be manually verified by measuring at least 3 complexes with the ECG and determining the average QTcF. If QTcF prolongation is ≥ Grade 3, an ECG may need to be repeated more frequently during a patient's visit, depending on the degree of the prolongation, as indicated in Table 7 and per institutional standards.

Note: Dose modification will be based on the average QTcF using the manual measurements.

Confidential and Proprietary

If the Investigator has any question regarding the local automated reading, a local cardiologist should be consulted. Treatment guidelines for patients experiencing QTc prolongations are provided in (Table 7).

Patients who experience \geq Grade 3 QTc prolongation must be assessed by the Investigator (or qualified designee) prior to discharge.

Table 7: Treatment Guidelines for QTc Prolongation

QTc Prolongation	After Tarloxotinib Administration		
Grade 1 450 to 480 msec QTcF	 Cycle 1 and Cycle 2 Day 1 May be discharged if the 4-hour (or later) post-infusion QTcF is Grade 1 or lower and asymptomatic After Cycle 2 Day 1 Obtain pre-infusion and 2-hour post-infusion ECGs May be discharged if the 2-hour (or later) post-infusion QTcF is ≤ Grade 1 and the patient is asymptomatic 		
Grade 2 481 to 500 msec QTcF	 Continue the same tarloxotinib dose for subsequent cycles Cycle 1 and Cycle 2 Day 1 May be discharged if the 4-hour (or later) post-infusion QTcF is ≤ Grade 2 and the patient is asymptomatic After Cycle 2 Day 1 Obtain pre-infusion and 2-hour post-infusions ECGs May be discharged if the 2-hour or later post-infusion QTcF is ≤ Grade 2 and the patient is asymptomatic Continue the same tarloxotinib dose for subsequent cycles 		
Grade 3 ≥ 501 msec QTcF	 Obtain ECGs every 15 to 30 minutes until QTcF is ≤ Grade 2 and then obtain ECGs every 1 hour May be discharged home if 2 subsequent measurements (at least 15 minutes apart) after the 4-hour post-infusion QTcF is ≤ Grade 2 and no significant arrhythmias If QTcF is ≥ 601 msec, permanently discontinue tarloxotinib If QTcF ≥ 501 msec and ≤ 600 msec Resume tarloxotinib dosing with dose reduction 1st occurrence: reduce to 100 mg/m² 2nd occurrence: reduce to 75 mg/m² 3rd occurrence: permanently discontinue tarloxotinib Obtain ECGs prior to and hourly (for at least 4 hours) following the next tarloxotinib infusion 		
Grade 3 > 60 msec increase from pre-infusion QTcF AND ≤ 500 msec QTcF	 Obtain ECGs every 15-30 minutes until QTcF is ≤ Grade 2 and then obtain ECGs every 1 hour May be discharged home if 2 subsequent measurements (at least 15 minutes apart) after the 4-hour post-infusion QTcF is ≤ Grade 2 and no significant arrhythmias Obtain ECGs prior to and hourly (for at least 4 hours) following the next tarloxotinib infusion 		
Grade 4 TdP or polymorphic ventricular tachycardia, signs/symptoms of serious arrhythmia	Place patient on telemetry and obtain ECGs as clinical indicated Obtain Cardiologist consult and admit to hospital for extended observation on telemetry Permanently discontinue tarloxotinib		

ECG = electrocardiogram; msec = millisecond; QTcF = corrected QT interval as calculated according to Fridericia's formula; TdP = Torsade de Pointes

Note: If QTcF prolongation is ≥ Grade 3, an ECG may need to be repeated more frequently during the patient's

Confidential and Proprietary

visit depending on the degree of the prolongation and per institutional standards.

Treatment and retreatment guidelines in this study are based on absolute QTcF observations that vary from the NCI CTCAE. Importantly, dose reductions are not based on the QTcF change from baseline, only the absolute QTcF. For example, if a patient has a change > 60 msec from baseline but has an absolute QTcF ≤ 500 msec, no dose reduction is required.

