6.9.2 Treatment Period

The following will be assessed or measured at the indicated study days:

Day 1

- Complete physical examination
- ECOG (Cycle 1)
- Weight
- Vital signs
 - o Pre-infusion
 - End of infusion (EOI)
 - \circ 30, 60, and 90 minutes after EOI (\pm 10 minutes)
- ECG (12-lead)
 - o Cycle 1
 - Pre-infusion
 - EOI
 - 1, 2, 3, and 4 hours after EOI (\pm 10 minutes)
 - Hourly thereafter as needed (see Section 6.9.2.1)
 - o Cycle 2
 - Pre-infusion

Confidential and Proprietary

Rain Therapeutics Inc.

- EOI
 1, 2, 3, and 4 hours after EOI (± 10 minutes)
- Hourly thereafter as needed (see Section 6.9.2.1)
- o Cycles 3+
 - Pre-infusion
 - 2 hours after EOI (± 10 minutes)
 - 4 hours after EOI (patients with QTcF \geq 501 msec) (\pm 10 minutes)
 - Hourly thereafter as needed (see Section 6.9.2.1)
- Hematology panel
- Serum chemistry panel
- Serum potassium (Cycles 1 and 2 only)
 - o EOI
 - o 3 hours after EOI (\pm 10 minutes)
- Urinalysis
- Pregnancy test
 - Urine (dipstick allowed)
- PK samples (Cycles 1 and 2 only)
 - o Pre-infusion (± 5 minutes)
 - \circ EOI (\pm 5 minutes)
 - o 3 hours after EOI (\pm 10 minutes)
 - o 7 hours after EOI (in a subset of patients on Cycle 1 Day 1 only) (\pm 10 minutes)
- Blood sample for biomarkers (e.g., ctDNA) (Cycles 1 and 2)
- Ensure that all electrolytes are within normal ranges
- Potassium supplementation, if applicable (See Table 5)
- Premedication, as applicable per local institutional guideline
- Tarloxotinib infusion (at least 1 hour in duration)
- Concomitant medications
- Assess AEs

Days 8, 15, and 22

- Vital signs
 - Pre-infusion
 - o EOI
 - \circ 30, 60, and 90 minutes after EOI (\pm 10 minutes)
- ECG (12-lead)

Confidential and Proprietary

- o Cycle 1
 - Pre-infusion
 - EOI
 - 1, 2, 3, and 4 hours after EOI (\pm 10 minutes)
 - Hourly thereafter as needed (see Section 6.9.2.1)
- o Cycles 2+
 - Pre-infusion
 - 2 hours after EOI (± 10 minutes)
 - 4 hours after EOI (patients with \geq Grade 3 QTcF prolongation) (\pm 10 minutes)
 - Hourly thereafter as needed (see Section 6.9.2.1)
- Serum chemistry panel
- Urinalysis (Cycle 1 only)
- Optional tumor biopsy
 - o Day 15 after EOI (preferred) or Day 16 (within 24 hours of any EOI)
 - Plasma samples for PK and biomarkers should be obtained as close to the time of biopsy as possible
- Ensure that all electrolytes are within normal ranges
- Potassium supplementation, if applicable (See Table 5)
- Premedication, as applicable per local institutional guideline

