## 6.3.2.4 Electrocardiograms

All 12-lead ECG tracings were performed once at the following visits: Screening, EOT, and Safety Follow-up. During Cycle 1, ECGs were performed at five time points (preinfusion, end of infusion [EOI], 1 hour after EOI, 2 hours after EOI, 3 hours after EOI, 4 hours after EOI), and hourly thereafter as needed. After Cycle 1, all treatment visits have ECGs performed at a minimum of three time points (preinfusion, 2 hours after EOI, 4 hours after EOI) and hourly thereafter as needed, as shown in Table 2.

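### The QTc categories in SAP 14.4 and protocol 9.7.1 leave out exactly 450 msec; as a lesser point, an infusion allowed at 450 to 500 msec carries no closer ECG follow-up

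*Protocol*

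**What the plan says.** **Categories.** SAP 14.4 and protocol 9.7.1 both plan counts and percentages of patients by absolute QTc at each ECG time and overall. As printed, the four categories are < 450, 451 to 480, 481 to 500 and ≥ 501 msec. Protocol Tables 7 and 12 grade 450 to 480 msec as Grade 1, 481 to 500 as Grade 2 and ≥ 501 as Grade 3. The Amendment 3 entry in the document history says that the 9.7.1 thresholds were revised to agree with NCI CTCAE grading.

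**Infusing at 450 msec or above.** Protocol 6.7.1, item 1b, states: "All patients must have a pre-infusion QTcF of < 450 msec by either" an automated or a manual reading. If the manual reading is 450 msec or more, the Medical Monitor is contacted to discuss its clinical significance and "to determine if it is appropriate to move forward with the infusion". Section 6.5 likewise sends any missed retreatment criterion to the Medical Monitor, with a change of dose or schedule, or stopping, as the matters to discuss. Neither section mentions ECG follow-up for an infusion that then goes ahead.

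**ECGs and discharge.** In Cycle 1 and on Cycle 2 Day 1, section 6.9.2 schedules ECGs at the end of infusion and at 1, 2, 3 and 4 hours. At later visits it schedules one at 2 hours, adds a 4-hour ECG only for patients at ≥ 501 msec or with Grade 3 prolongation, and allows hourly ECGs after that as needed. For Grade 1 at later visits, Table 7 says: "May be discharged if the 2-hour (or later) post-infusion QTcF is ≤ Grade 1 and the patient is asymptomatic". The Grade 2 row gives the same rule with Grade 2 as the limit. After a Grade 3 event the instruction is: "Obtain ECGs prior to and hourly (for at least 4 hours) following the next tarloxotinib infusion".

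**The concern.** QT prolongation is the main identified risk of this drug, and the SAP is meant to support a comprehensive safety analysis. A category table that skips the value at which Grade 1 begins does not agree with the grading in its own protocol. At any time point where a patient reads 450 msec, the four counts fall short of the number measured. That value is also the first to fail the pre-infusion limit.

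The secondary concern is one of conduct. A pre-infusion QTcF of 450 msec or more is treated as a reason not to infuse without discussion. Once the infusion is allowed, however, the required follow-up is the same as for a patient who met the limit. Section 2.5 says that patients are watched for the whole period at risk, and section 2.6 reports prolongation up to 4 hours after the infusion ends. A patient infused with less room below 501 msec could leave at 2 hours. A later rise to 501 msec would then go unrecorded, as would the dose reduction and the hourly ECGs at the next infusion that it should trigger.

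**Working it through.** The plan gives no figure of its own to reproduce here, so this is a check of thresholds and schedules.

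**Categories.** The check assumes that QTcF is recorded in whole milliseconds.

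| QTcF (msec) | As printed, SAP 14.4 and protocol 9.7.1 | If the first limit were ≤ 450 | Tables 7 and 12 | Proposed |
|---|---|---|---|---|
| 449 | < 450 | ≤ 450 | below Grade 1 | < 450 |
| 450 | none | ≤ 450 | Grade 1 | 450 to 480 |
| 451 | 451 to 480 | 451 to 480 | Grade 1 | 450 to 480 |

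Over all whole values from 400 to 620 msec, the printed categories miss only 450. The grading limits and the proposed categories miss none. The upper two categories already match Grades 2 and 3.

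**Which infusions the secondary point covers.** Extra ECGs under Table 7 and section 6.9.2.1 start at ≥ 501 msec, at a rise of more than 60 msec, or after a Grade 3 event at a previous infusion. The gap is therefore limited to pre-infusion readings of 450 to 500 msec, after Cycle 2 Day 1, in patients without such a trigger.

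**Number of ECGs and length of stay.**
- Required post-infusion ECGs at those visits (6.9.2): 1, at 2 hours.
- Table 7 schedule after Grade 3: 4, at 1, 2, 3 and 4 hours.
- Difference: 4 − 1 = 3. SAP 6.3.2.4 describes a 4-hour ECG at every treatment visit after Cycle 1. If that was routine, the difference is 4 − 2 = 2.
- Extra stay: 4 − 2 = 2 hours.
- In Cycle 1 and on Cycle 2 Day 1, all four times are already scheduled, so nothing is added.

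**Timing.** The latest prolongation in section 2.6 is 4 hours after completion, which is 4 − 2 = 2 hours after the earliest permitted discharge.

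**Room below Grade 3.** The rise needed to reach 501 msec is 501 − 450 = 51 from 450, 501 − 470 = 31 from 470, and 501 − 490 = 11 from 490. Section 2.3.2 reports mean maximum rises of 51 msec at 3 hours (TH-CR-601) and 55 msec at 2 hours (TH-CR-602) after the end of infusion. Starting from 450, these give 450 + 51 = 501 and 450 + 55 = 505. They are means from other patients on Cycle 1 Day 1, so they illustrate the margin and do not predict what happens at later infusions.

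**The case against.** **On the categories.** The printed sign may be a reading error. In the text available, the first two lines of the list in protocol 9.7.1 are visibly misread, and the top change category in SAP 14.4 has lost its sign. A first limit of ≤ 450 would leave no gap. This is plausible, especially for 9.7.1, and it stands as a reason not to call the gap certain. It does not rescue the second category. With ≤ 450, a Grade 1 reading is still counted as normal, against Tables 7 and 12 and against the stated purpose of the 9.7.1 revision. The objection that the effect is tiny also stands: it concerns one value in a descriptive table, and SAP 14.4 lists QTcF in any case.

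**On the ECGs.** Most of the objection stands. The 2-hour rule applies to every later infusion and is not created by the Medical Monitor route. Discharge is permitted, not required, and needs the patient to be free of symptoms. The Medical Monitor can ask for more ECGs case by case, and 6.9.2 already provides for hourly ECGs as needed. On schedule, a patient reaching this stage has had five infusions with ECGs to 4 hours (Cycle 1 Days 1, 8, 15 and 22, and Cycle 2 Day 1). In TH-CR-602, the larger earlier study (30 patients against 21), the mean peak came at 2 hours. What remains is that nothing beyond the ordinary schedule is required when the limit is waived.

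**Stronger readings.** A reader might infer that 6.7.1 contradicts itself by setting a limit and then allowing infusion above it. The text describes a limit with a central exception, consistent with 6.5. A reader might also infer that patients were infused above the limit and sent home too early. The documents give no count of such infusions and no resulting harm.

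**Conclusion.** The categories are wrong as written, and the error is minor. As printed, 450 msec falls in 0 of 4 categories; with ≤ 450 it falls in the wrong one. The conclusion holds on either reading of the sign and assumes whole-millisecond values. The effect on the report cannot be sized, because the number of readings at exactly 450 msec is not given.

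The ECG point is an optional improvement and not an error. It covers only infusions allowed at 450 to 500 msec after Cycle 2 Day 1. It rests on protocol 6.9.2 and Table 7 as the rules for conduct, since the SAP, with its description of a routine 4-hour ECG, was written after database lock. The study was discontinued and the database locked on 23 April 2021, so this part matters only if the protocol is used again.

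**What to change.** 1. In SAP 14.4, make the first two absolute categories < 450 msec and 450 to 480 msec. The SAP governs the report. Make the same change in protocol 9.7.1 for consistency. The cost is two category limits in each document, plus a rerun of the QTcF category table if it already exists. No new data are needed, and nothing is counted twice.

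2. Only if the protocol is re-used, add to 6.7.1 that any infusion the Medical Monitor allows at a manually read pre-infusion QTcF of 450 msec or more follows the schedule Table 7 already sets after a Grade 3 event. That means ECGs hourly for at least 4 hours, with no discharge before the 4-hour ECG. The Medical Monitor's discretion is kept and no infusion is lost. For such infusions after Cycle 2 Day 1, the cost is up to 3 more ECGs (2 if a 4-hour ECG is already routine) and about 2 hours longer on site.

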Study TH-CR-602 enrolled 30 patients. In combining the results of both studies, the most common AE was ECG QT prolongation, which occurred in 35/51 (68.6%) of the patients and in these 35 patients, 19 (54.3%) were Grade 3 severity and 16 (45.7%) less than Grade 3. Skin and subcutaneous tissue disorders were experienced by patients and the most frequent were dermatitis acneiform 13/51 (25.5%), rash 7/51 (13.7%), and pruritus 5/51 (9.8%) and most were \leq Grade 2 in severity. The other most common treatment-related AEs were diarrhea (35.3%, 18/51) and fatigue (17/51, 33.3%).

Special emphasis was placed on QT monitoring in both studies. This included Holter monitoring during Cycle 1 Day 1 and calibrated ECG machines with central reading of ECG measurements throughout the study duration. Holter monitoring was used to record and extract triplicate QT measurements at 9 predefined time points during the first 24 hours of Cycle 1 Day 1 in both studies. The mean maximum QTcF change from baseline was 51 msec occurring 3 hours after the end of infusion and 55 msec occurring 2 hours after the end of infusion in Study TH-CR-601 and Study TH-CR-602, respectively. Across the 2 studies, 10 patients (21%) developed QTcF values \geq 501 msec and 16 patients (34%) developed a QTcF change from baseline of > 60 msec. The time-matched PK and QTcF data suggest a QT prolongation hysteresis of up to 2 to 3 hours after the tarloxotinib C_{max} which occurs at the end of infusion. T-wave segmentation analysis suggests that tarloxotinib is a hERG channel blocker and that it does not possess mitigating multichannel blocking properties.

Please refer to the Tarloxotinib Investigator's Brochure for the most current safety assessment.

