6.9.2.1 Electrocardiogram Guidance for QT Prolongation During the Treatment Period

In the event of QTcF prolongation (\geq 501 msec or > 60 msec increase compared to pre-infusion), repeat ECG every 15 to 30 minutes until resolved to Grade 2 (481 to 500 msec) or lower (\leq 480 msec) and then obtain ECGs every hour. For patients who have had a Grade 3 event of

Confidential and Proprietary

QTcF prolongation at a previous infusion ECGs should be conducted hourly for the 4 hours following the subsequent infusion.

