8.5 Reporting QTc Prolongation

QT prolongation is not unexpected but it is an AE of special interest (AESI). Grade 3 AESIs require expedited reporting to the Sponsor. ECGs will be obtained throughout the study and will be read locally at the investigational sites. Grade 3 QTc prolongation (absolute QTcF of \geq 501 msec or QTcF increase of > 60 msec relative to pre-infusion) or Grade 4 QTc prolongation will be reported as an AESI.

Any apparent Grade 3 AESIs should be verified by manually measuring at least 3 complexes within the ECG and determining the average QTcF.

AESIs will be reported by submitting an AESI Report to:

[contact]

All events of Grade 3 QTc prolongation (absolute QTcF of \geq 501 msec or QTcF increase of \geq 60 msec relative to pre-infusion) or Grade 4 QTc prolongation will be reported as an AESI unless the event met the criteria of serious (see Section 8.1.1.4) in which case it will be reported as an SAE.

Confidential and Proprietary

Table 12: NCI CTCAE Grading of ECG QTc Prolongation (Medical Dictionary of Regulatory Activities Code: 10014383)

ECG QTc Prolongation NCI CTCAE Grade					
1	2	3	4	5	
Average QTc	Average QTc	Average	Torsade de Pointes	Not applicable	
450 to 480 msec	481 to 500 msec	$QTc \ge 501 \text{ msec}$	OR		
		OR	polymorphic		
		> 60 msec change	ventricular		
		from baseline*	tachycardia		
			OR		
			signs/symptoms of		
			serious arrhythmia		

Adapted from NCI CTCAE v5.0

ECG = electrocardiogram; NCI CTCAE = National Cancer Institute Common Terminology Criteria for Adverse Events; QTc = corrected QT interval; QTcF = corrected QTc interval as calculated according to Fridericia's formula

Definition of QTc prolongation: A finding of a cardiac dysrhythmia characterized by an abnormally long QTc * Although a Grade 3 event (≥ 501 msec OR > 60 msec change from baseline) is reportable as an adverse event of special interest, dose reductions are not required for patients with absolute QTcF ≤ 500 msec and a ≤ 60 msec QTcF change from baseline.

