8.7 Electrocardiogram Monitoring

Standard 12-lead ECGs will be performed locally using a calibrated digital ECG machine capable of providing automated measurements. All ECG tracings will be acquired with the patient in the supine position after the patient has been resting for at least approximately 5 minutes. ECG tracings will be measured and interpreted locally by a cardiologist or other qualified health care professional in accordance with institutional standard of care.

Immediate medical management of patients will be based on the automated reading obtained at the investigational site (all clinically significant ECG readings should be manually verified by a qualified individual). If the Investigator has any question regarding the local automated read, a local cardiologist should be consulted.

Confidential and Proprietary

For patients with QT prolongation during tarloxotinib infusion, ECGs may need to be conducted more frequently than indicated in the Schedule of Events, depending on the degree of prolongation (see Section 6.9.2.1).

Rain will review all reported ECG measurements at least quarterly.

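### Verifying a > 60 msec QTcF rise requires a manual reading of the flagged ECG only, so a manual value can be compared with an automated pre-infusion value

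*Protocol*

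**What the plan says.** Protocol 6.7.1 item 2 defines Grade 3 by either limb, the absolute value or the rise, and says the event "will be manually verified by measuring at least 3 complexes with the ECG and determining the average QTcF". Section 8.5 repeats the instruction for reporting adverse events of special interest (AESIs): "Any apparent Grade 3 AESIs should be verified by manually measuring at least 3 complexes". Both speak of a single ECG.

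For the pre-infusion tracing, 6.7.1 item 1 asks for a manual reading only if the automated QTcF is 450 msec or more. Otherwise the first accepted source is "Calculation using the automated measurements of the first ECG or".

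Section 8.7 has tracings measured and interpreted locally by a qualified person and asks for manual verification of clinically significant readings. It also says: "Immediate medical management of patients will be based on the automated reading obtained at the investigational site". Section 6.5 and the note in 6.7.1 make the manual average decisive for dose modification. Dose reductions depend on absolute QTcF only (end of 6.7.1).

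I found nothing in Protocol 6.5, 6.9.2.1, 8.7 or 9.7.1, or in SAP 14.4, that requires a manual pre-infusion value below 450 msec.

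**The concern.** One tracing settles the absolute limb. The rise needs two, and the plan specifies how only the second is checked. If the first stays automated, two errors can enter:

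- A systematic difference between methods no longer cancels. If automated readings run longer than manual ones, true rises are removed. If they run shorter, false flags tend to be confirmed.
- A chance error in the automated pre-infusion value that helped to cause the flag is used again in the check, so verification is not independent of what it verifies.

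This limb is the commoner one. Across the two earlier phase 2 studies "16 patients (34%) developed a QTcF change from baseline of > 60 msec", against 21% reaching 501 msec or more (Protocol 2.3.2). It decides four things:

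- whether an AESI report is filed;
- the Grade 3 counts in the SAP's severity tables (SAP 14.1, 14.1.2);
- discharge. Table 7 asks for two readings after the 4-hour ECG for Grade 3. For lower grades one reading is enough, at 4 hours in Cycle 1 and on Cycle 2 Day 1, and at 2 hours thereafter;
- ECGs at the next infusion. Section 6.9.2.1 says that after Grade 3 "QTcF prolongation at a previous infusion ECGs should be conducted hourly for the 4 hours following the subsequent infusion".

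**Working it through.** **1. Does the 450 msec trigger cover these events?** Table 7's second Grade 3 row covers a rise above 60 msec with QTcF at or below 500 msec. The pre-infusion value is then below 500 − 60 = 440 msec, so the trigger cannot fire.

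**2. Where can next-infusion ECGs be lost?** Section 6.9.2 already schedules ECGs "1, 2, 3, and 4 hours after EOI" at every Cycle 1 infusion and on Cycle 2 Day 1 (infusions 1 to 5). Events at infusions 1 to 4 are therefore followed by a fully monitored infusion. Only events at infusion 5 or later matter, out of up to 10 × 4 = 40 expected infusions (11.3). From then on, a removed event leaves the next infusion with its 2-hour ECG and without those at 1, 3 and 4 hours. If the schedule described in SAP 6.3.2.4 applies, which gives a 4-hour ECG to all, only the 1- and 3-hour ECGs are lost. The mean maximum rises in the two earlier studies were 51 msec, "occurring 3 hours after the end of infusion and 55 msec occurring 2 hours after the end of infusion", so a 2-hour ECG covers one pattern and not the other.

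**3. Which errors cancel?** Let R be the true rise. An automated reading is truth + d + a, where d is the automated-minus-manual offset and a is random error. A manual average is truth + m. Subscripts 0 and 1 mean before and after infusion.

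- Flag: automated − automated = R + a₁ − a₀ > 60
- Literal rule: manual − automated = R + m₁ − a₀ − d > 60
- Paired rule: manual − manual = R + m₁ − m₀ > 60

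d cancels in the flag and the paired rule, but not in the literal rule. a₀ is shared by the flag and the literal rule.

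**4. Illustration of size.** The plan states no figure to reproduce. From 2.3.2, the pooled mean rise is (51 × 21 + 55 × 30)/51 = 53.4 msec. Setting P(R > 60) = 0.34 gives SD = 6.65/0.4125 = 16.1 msec. Assumed, not from the documents: R is Normal, reading SD is 5 msec automated and 3 msec manual, and d ranges from −10 to +10 msec. Simulation of 4,000,000 draws, among flagged events:

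| Rule | Misclassified | True rises removed | False flags confirmed |
|---|---|---|---|
| Paired, any d | 10.4% | 7.8% | 21.5% |
| Literal, d = −10 | 18.5% | 0.1% | 96.7% |
| Literal, d = −5 | 16.5% | 0.9% | 82.3% |
| Literal, d = 0 | 14.6% | 6.3% | 50.0% |
| Literal, d = +5 | 20.6% | 21.3% | 17.8% |
| Literal, d = +10 | 35.7% | 43.3% | 3.3% |

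Consistency check: if p is the share of flagged events that are true rises, 7.8p + 21.5(1 − p) = 10.4 gives p = 11.1/13.7 = 0.81. Then 0.81 × 6.3 + 0.19 × 50.0 = 14.6, as in the table.

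**5. Sensitivity.**

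- Automated/manual SDs of 5/3, 5/5, 8/5 and 10/5: paired 10.4% to 16.2% misclassified, literal 14.6% to about 36%. At 5/5 and d = −5 they are about level (16.2% against 16.6%).
- Manual noisier (5/8): paired 22.9%. The literal rule is better at d = −10, −5 and 0 (18.1%, 18.3%, 20.9%) and worse at +5 and +10 (27.3%, 37.4%).
- First study alone, using its own 38% with a rise above 60 msec (2.3.2) and mean 51, so SD 29.5: paired 5.7%, literal 7.9% at d = 0, a gap of 2.2 points.
- Under every SD pair tried, pairing removes more true rises than the literal rule when d is zero or negative.

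**The case against.** The strongest reply is that what must be verified is an increase, and verifying a difference ordinarily means checking both terms. The plan never prescribes a mixed comparison, and 8.7 already puts tracings before a qualified reader. That stands in part. A site may re-read both tracings, and a reader who infers that the protocol mandates a mixed comparison goes further than the text. What remains is that the paired reading is not required, and the literal instruction names one ECG.

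The second reply carries more weight: pairing is not uniformly safer. If automated readings run level with or shorter than manual ones, pairing discards more true rises. Over-reporting may be the preferable error for a drug with a known QT effect. Counting missed and false events equally hides this. It stands, and the cost has to be stated in full.

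Third, the harm is contained:

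- Dosing ignores this limb.
- Repeat ECGs under 6.9.2.1 have no stated manual step, and same-day management starts from the automated reading.
- The sponsor reviews ECG measurements at least quarterly (8.7).
- SAP 14.4 tabulates QTcF change whatever the AESI status.

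These stand as partial backstops. Quarterly review comes too late to restore ECGs at the next weekly infusion.

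Finally, SAP section 4 records that the study was discontinued for business reasons, with 41 subjects enrolled and the database locked on 23 April 2021. No infusion remains for a new sentence to affect.

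**Conclusion.** The gap is real but small. For a rise above 60 msec with QTcF at or below 500 msec, the text allows a manual value to be checked against an automated one. An offset between methods then passes through, and the automated error behind the flag is reused. The ≥ 501 msec limb rests on one tracing and is unaffected.

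In the base case the literal rule misclassifies 14.6% to 35.7% of flagged events, depending on offset, against 10.4% with pairing. These are illustrations. The sign and size of any offset, and both reading SDs, are unknown. The rises modelled are Cycle 1 Day 1 values, and the documents give none for the later period in which next-infusion ECGs can be lost. The benefit also assumes that manual averages are no noisier than automated readings.

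A reader might infer that Grade 3 counts in this trial are wrong, that events were missed, or that doses were affected. The documents support none of these. They do not show how sites read the pre-infusion tracings, and this limb never changes dose. Effects are limited to AESI reports, Grade 3 counts, discharge readings and, for events from Cycle 2 Day 1 onward, the next infusion's hourly ECGs. Efficacy is unaffected. This is a low-cost improvement at the lowest severity.

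**What to change.** Add one sentence to 6.7.1 item 2 and to 8.5: *When verifying a > 60 msec increase, also manually measure at least 3 complexes of the same infusion's pre-infusion ECG, and grade the increase on the two manual averages.* No other section changes. With this trial closed, it serves any protocol that reuses the wording.

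The direct cost is one extra manual measurement of an existing tracing per infusion flagged for a > 60 msec rise, with no added ECGs, visits or staff.

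The statistical cost depends on the offset (base case):

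- **Automated not longer than manual:** pairing removes 7.8% of true rises, against 6.3% at no offset, 0.9% at −5 msec and 0.1% at −10 msec. In exchange it confirms 21.5% of false flags, against 50.0%, 82% and 97%.
- **Automated longer:** pairing removes far fewer true rises, 7.8% against 21.3% at +5 msec and 43.3% at +10 msec. It confirms somewhat more false flags, 21.5% against 17.8% and 3.3%.
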